2.8.4.2 Vital signs

Vital sign assessments are performed in order to characterize basic body function. The following parameters are being collected: height (cm), weight (kg), body temperature (°C), pulse rate (beats per minute), systolic and diastolic blood pressure (mmHg).

Data handling

Vital signs collected on treatment will be summarized. Values measured outside of on-treatment period will be flagged in the listings.

Data analysis

For analysis of vital signs the clinically notable vital sign criteria are provided in Table 2-12 Criteria for notably abnormal vital signs below.

 Table 2-12
 Criteria for notably abnormal vital signs

	Clinically notable criteria	
Vital sign (unit)	High	Low
Systolic blood pressure [mmHg]	≥ 95th percentile of the age and height group ¹	≤ 5th percentile of the age and height group ¹

	Clinically notable criteria			
Vital sign (unit)	High		Low	
Diastolic blood pressure [mmHg]	≥ 95th percentile of the age and height group ¹		≤ 5th percentile of the age and height group ¹	
Body temperature [°C]	≥ 38.4°C		≤ 35.	.0°C
Pulse rate [bpm] ²	12-18 months	> 140	12-18 months	< 103
	18-24 months	> 135	18-24 months	< 98
	2-3 years	> 128	2-3 years	< 92
	3-4 years	> 123	3-4 years	< 86
	4-6 years	> 117	4-6 years	< 81
	6-8 years	> 111	6-8 years	< 74
	8-12 years	> 103	8-12 years	< 67
	12-15 years	> 96	12-15 years	< 62
	≥ 15 years	> 92	≥ 15 years	< 58
Weight	increase from baseline of ≥ 2 BMI-for-age percentile categories ³		decrease from b BMI-for-age per categories ³	

bpm=beats per minute; CDC= Centers for Disease Controls and prevention; NHLBI= National Heart, Lung, and Blood Institute;

¹ Blood pressure percentiles are calculated for each blood BP record using the method described in Appendix B of the following reference: The Fourth Report on Diagnosis, Evaluation and Treatment of High Blood Pressure in Children and Adolescents. Pediatrics 2004; 114; 555.

² Fleming S, Thompson M, Stevens R, et al. Normal ranges of heart rate and respiratory rate in children from birth to 18 years of age: a systematic review of observational studies. Lancet 2011; 377: 1011-18.

³ BMI-for-age percentiles categories (P3, P5, P15, P25, P50, P75, P85, P95, P97) are obtained from the WHO Growth Charts (http://www.who.int/childgrowth/en/);

Note: For patients less than 2 years old, growth charts are based on recumbent length instead of height, which is not collected in the study. As an approximation, height collected in the study is considered as equal to the recumbent length; for patients over 228 months- old, percentiles are not available and will be considered as missing.

The number and percentage of patients with notable vital sign values (high/low) will be presented.

Vital signs shift table based on values classified as notable low, normal, notable high or notable (high and low) at baseline and worst post-baseline will be produced for pulse rate, diastolic BP and systolic BP. Baseline is defined as the last non-missing value prior to or coinciding with first dose. The worst post-baseline value refers to the worst post-baseline value on treatment.

Descriptive statistics (mean, median, standard deviation, minimum and maximum) will be tabulated for baseline, at each post-baseline time point and changes from baseline at each postbaseline time point for each vital sign measure. For each parameter, only patients with a value at both baseline and post baseline (on treatment) will be included. For pulse parameter, the subject can be counted in both low and high categories and with a subject contributing to multiple age categories as data is collected over time.

Novartis	Confidential	Page 39
SAP Final Analysis HGG		CDRB436G2201

A listing of all vital sign assessments will be produced by and notable values will be flagged. A separate listing of only the patients with notable vital sign values may also be produced. In the listing, the assessments collected outside of on-treatment period will be flagged.

2.8.4.3 **Performance status**

The Karnofsky and Lansky performance status scale (Table 2-13 Performance status criteria) will be used to assess physical health of patients.

•	RMANCE STATUS CRITERIA sky and Lansky performance scores are	e intende	d to be in multiples of 10
Karnofsky (age >16 years of age)		Lansky	/ (age <16 years)
Score	Description	Score	Description
100	Normal, no complaints no evidence of disease.	100	Fully active, normal.
90	Able to carry on normal activity, minor signs of symptoms of disease.	90	Minor restrictions in physically strenuous activity.
80	Normal activity with effort, some signs of symptoms of disease.	80	Active, but tires quickly.
70	Cares for self, unable to carry on normal activity or do active work.	70	Both greater restriction of and less time spent in play activity.
60	Requires occasional assistance, but is able to care for most of his/her needs.	60	Up and around, but minimal active play, keeps busy with quieter activities.
50	Requires considerable assistance and frequent medical care.	50	Gets dressed, but lies around much of the day; no active play, able to participate in all quiet play and activities.
40	Disabled, requires special care and assistance.	40	Mostly in bed, participates in quiet activities.
30	Severely disabled, hospitalization indicated. Death not imminent.	30	In bed, needs assistance even for quiet play.
20	Very sick, hospitalization indicated. Death not imminent.	20	Often sleeping; play entirely limited to very passive activities.
10	Moribund, fatal processes progressing rapidly.	10	No play, does not get out of bed.

[figure not shown]
 Table 2-13
 Performance status criteria

Frequency counts and percentages of patients in the score category of 100, 90, 80, 70, and < 70 will be provided by time point based on the windows defined in Section 2.1.1. A summary of change from baseline by scheduled visits will be performed, as well as the worst case post-baseline (lowest value during the on-treatment period) and the best case post-baseline (highest value during on-treatment period) changes during the study.

A supporting listing will also be provided.

2.8.4.4 Dermatological Evaluation

Skin examination results will be summarized by frequency counts and percentages of patients in each category (normal, abnormal) by scheduled time points. A supporting listing will also be provided.

2.8.4.7 Growth and development (Height and Weight)

Growth data consist of height, BMI, height SDS, BMI SDS, height velocity SDS, weight velocity SDS, height velocity and weight velocity.

Height and weight will be summarized at 6-month intervals during the on-treatment period, using the standard deviation scores (SDS, also called Z-score), velocity and velocity SDS. The relevant height and weight values for each 6-month period are defined using time windows, as defined in Table 5-4. The Z-scores will allow identification of potential outliers.

The formula used to calculate the SDS and height and weight velocities are provided in the Appendix 5.4.2.

Novartis	Confidential	Page 42
SAP Final Analysis HGG		CDRB436G2201

Note that BMI SDS are reported instead of weight SDS as no reference data for weight are provided by the WHO for age beyond 10.

Height and BMI SDS and height and weight velocity SDS will be summarized using descriptive statistics (mean, standard deviation, median, Q1, Q3, minimum, maximum) for each time window (at baseline and thereafter allowing informal comparison of growth data), as well as by presenting number of patients with SDS values lower/higher than 5th/95th percentiles respectively.

Box plots will be plotted for each time window. A shift table to compare baseline SDS to the worst on-treatment SDS categorized as Low (SDS < -1.645), High (SDS > 1.645) or Normal (-1.645 \leq SDS \leq 1.645) will be produced for height and BMI SDS. Another shift table to compare the baseline height SDS to the last available on-treatment height SDS categorized according to the main percentile lines (>95th, 95th to 90th, 90th to 75th, 75th to 50th, 50th to 25th, 25th to 10th, 10th to 5th and \leq 5th percentile) will be produced.

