5.4.1 Growth data

SDS will be calculated using the current formulae provided by the WHO as follows:

- $\frac{\left(\frac{X}{M}\right)^{L}-1}{2}$
- 1. Calculate $z_{ind} = LS$
- $\begin{array}{ll} \text{2.} & \text{If} \mid z_{\text{ind}} \mid \leq 3, & \text{SDS} = z_{\text{ind}} \\ & \text{If} \; z_{\text{ind}} > 3, & \text{SDS} = 3 + (X \text{SD3}pos) \ / \ \text{SD23}pos \\ & \text{If} \; z_{\text{ind}} < -3, & \text{SDS} = -3 + (X \text{SD3}neg) \ / \ \text{SD23}neg \\ \end{array}$

where:

- X is height in centimeters or BMI in kilograms/ m^2 ,
- *L*, *M* and *S* are height or BMI-, sex- and age-specific reference values from the WHO Growth Charts.
- SD3*pos* is the cutoff 3SD calculated by the LMS method: SD3*pos* = M * $(1 + LS*3)^{1/L}$
- SD3*neg* is the cutoff -3SD calculated by the LMS method: SD3*neg* = M * $(1 + LS^*(-3))^{1/L}$
- SD23*pos* is the difference between the cutoffs 3SD and 2SD: SD23*pos* = M * $(1 + LS*3)^{1/L}$ - M * $(1 + LS*2)^{1/L}$
- SD23*neg* is the difference between the cutoffs -2SD and -3SD: SD23*neg* = M * $(1 + LS^*(-2))^{1/L}$ - M * $(1 + LS^*(-3))^{1/L}$

Height-for-age and BMI-for-age L, M and S reference values for males and females are available under [http://www.who.int/childgrowth/standards/en/] (for patients aged between 0 to 5 years old) and [http://www.who.int/growthref/en/] (for patients aged between 5 to 19 years old). Note: use age in months at time of assessment "(visit date – date of birth) / 30.4375" rounded to the nearest whole month for corresponding values of L, M and S. These correspond to the latest available international references available at this time and described in the 2007 Bulletin of the WHO [Mercedes de Onis et al 2007]. SDS is actually a Z score that measures the distance from the population mean in units of standard deviations. That is, SDS < 0 refers

Novartis	Confidential	Page 50
SAP Final Analysis HGG		CDRB436G2201

to values lower than the population mean, and for example SDS \leq -1.645 refers to values in the lowest 5%.

The SDS score can be converted to a percentile assuming a standard normal distribution [mean=0, standard deviation =1]. Note that BMI is reported instead of weight as no reference data are provided by the WHO for age beyond 10.

Height velocity is defined as follows:

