Height velocity (cm/6-months) = (height in time window k – height in time window k-1) ÷ ([assessment date in time window k – assessment date in time window k-1] ÷ [365.25/2]), and similarly for weight velocity.

Velocity SDS is calculated as (velocity – mean) / standard deviation, where mean and standard deviation are obtained as the height-, weight-, sex- and age-specific values [Baumgartner et al 1986], where the age category immediately above the patient's exact age (at the assessment date in time window k) should be used. Velocity SDS will only be calculated for time window k if data also exists for time window k-1, since calculating across multiple units of 6 months requires more than one reference value to be taken into account.

Table 5-4 summarizes the time windows for growth data, where windows are centered at every 6 months after start of study treatment. Although height and weight are collected more frequently than every 6 months (post-enrollment), this choice of time window length was made to reflect the degree of accuracy in the reference values (every 6 months) that will be used in the calculation of summary variables of growth.

In case of multiple assessments falling into the time window interval, the closest to the target date will be considered. For example, If there are three assessments falling under the time window of Day 85 to 252, then the closest one to target day of 168 will be considered. If two assessments are equidistant from target date, the average will be considered of those respective assessments.

Planned assessment	Time window
Baseline	Days ≤1
Month 6 (Day 168)	Days 85 – 252
Month 12 (Day 336)	Days 253 – 420
Month 18 (Day 504)	Days 421 – 588
Month xx (Day xx * 28)	Days ((xx – 3) * 28 + 1) – Day ((xx + 3) * 28)
End of treatment (EoT)	Earliest data available on or after EoT date up to and including 30 days after EoT
Day 1 = date of first intake of study drug	
xx = Every 6 months	

Table 5-4Time windows for growth data (height SDS, height velocity, weight velocity, BMI SDS)

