2.8.4.7 Growth and development (Height and Weight)

Growth data consist of height, BMI, height SDS, BMI SDS, height velocity SDS, weight velocity SDS, height velocity and weight velocity.

Height and weight will be summarized at 6-month intervals during the on-treatment period, using the SDS, velocity and velocity SDS. The relevant height and weight values for each 6-month period are defined using time windows, as defined in Table 5-4. The z-scores will allow identification of potential outliers.

The formula used to calculate the SDS and height and weight velocities are provided in the Appendix 5.4.2.

Note that BMI SDS are reported instead of weight SDS as no reference data for weight are provided by the WHO for age beyond 10.

Height and BMI SDS and height and weight velocity SDS will be summarized using descriptive statistics (mean, standard deviation, median, Q1, Q3, minimum, maximum) for each time window (at Baseline and thereafter allowing informal comparison of growth data), as well as by presenting number of patients with SDS values lower/higher than $5^{th}/95^{th}$ percentiles respectively.

Box plots will be plotted for each time window. A shift table to compare baseline SDS to the worst on-treatment SDS categorized as Low (SDS <- 1.645), High (SDS > 1.645) or Normal (- $1.645 \le SDS \le 1.645$) will be produced for height and BMI SDS. Another shift table to compare the baseline height SDS to the last available on-treatment height SDS categorized according to the main percentile lines (>95th, 95th to 90th, 90th to 75th, 75th to 50th, 50th to 25th, 25th to 10th, 10th to 5th and \le 5th percentile) will be produced.

In addition, a mixed model will be used to estimate differences of change from baseline in height SDS between treatment groups. A mixed model with height SDS as the response variable and time, gender, and treatment as explanatory variables will be fit using PROC MIXED. See Appendix 5.4.5 for model specifications and further details.

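### By-window height and BMI SDS are compared with baseline as levels, not as change in the same patients, so selective loss of patients can move the mean when no child's SDS has changed

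*SAP*

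**What the plan says.** **By-window summary.** In the HGG final SAP, section 2.8.4.7: "Height and weight will be summarized at 6-month intervals during the on-treatment period". Height SDS, BMI SDS and the velocity SDS are then described "for each time window (at baseline and thereafter allowing informal comparison of growth data", with box plots per window. The LGG final SAP, section 2.8.4.7, has the same plan: "at Baseline and thereafter allowing informal comparison of growth data".

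**Paired analyses in the same section.** There are two shift tables. For height and BMI: "A shift table to compare baseline SDS to the worst on-treatment SDS", in three bands cut at ±1.645. For height only: "Another shift table to compare the baseline height SDS to the last available on-treatment height SDS categorized according to the main percentile lines", in eight bands.

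**Velocity.** Section 5.4.1 defines height and weight velocity between consecutive windows in the same patient: "Velocity SDS will only be calculated for time window k if data also exists for time window k-1".

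**Age limit.** The reference values used for SDS in section 5.4.1 come from one source for the youngest children and another "for patients aged between 5 to 19 years old". A note in section 2.8.4.2 says that "for patients over 228 months- old, percentiles are not available and will be considered as missing".

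**Vital signs.** Section 2.8.4.2 counts height and weight as vital signs and plans change from baseline at each time point, limited to patients with both values. Its notable-value table also flags moves between BMI-for-age percentile categories.

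**LGG only.** A mixed model for height SDS is specified in section 5.5.5.

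**The concern.** The SAP invites the reader to set each window's SDS against baseline. As written, the two rows can describe different children. The baseline row is not limited to those present later, so the natural reading is that it holds everyone with a baseline value. A later row holds only those still on treatment and still young enough to have a reference value. A difference between the rows then mixes two things: a real change in growth, and a change in who is measured. The artefact can go either way, so it could suggest an effect on growth or hide one.

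Raw height and weight do get paired change, but in growing children raw change largely reflects normal growth. The score that removes age and sex is the one left unpaired.

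**Working it through.** The plan gives no figure for this point, so there is none to reproduce.

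**1. Composition effect when no child's SDS changes.** Let f be the share of patients still in the window, and D the baseline mean SDS of stayers minus that of leavers.

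- All-patient baseline mean = f × (stayers' mean) + (1 − f) × (leavers' mean)
- Window mean = stayers' mean, because nobody changes
- Apparent change = window mean − baseline mean = (1 − f) × D

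f and D are assumptions; the SAP gives neither. Over a range, in SDS units:

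| Remaining (f) | D = 0 | D = 0.25 | D = 0.5 | D = 1.0 |
|---|---|---|---|---|
| 75% | 0 | 0.06 | 0.13 | 0.25 |
| 50% | 0 | 0.13 | 0.25 | 0.50 |
| 25% | 0 | 0.19 | 0.38 | 0.75 |

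For example, with half remaining and D = 0.5: 0.5 × 0.5 = 0.25. A simulation (N = 40, SD 1, 20,000 runs) agrees: 0.124, 0.250 and 0.374 for D = 0.5.

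**2. Chance movement when loss is unrelated to SDS.** The expected shift is 0, but with m of N patients left the chance SD is √(1/m − 1/N), taking the SDS standard deviation as 1. N = 40 is the planned HGG size in section 1.1.

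- m = 30: √(1/30 − 1/40) = 0.09
- m = 20: √(1/20 − 1/40) = 0.16
- m = 10: √(1/10 − 1/40) = 0.27

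**3. Paired change.** If each child is compared with his or her own baseline, the composition effect is exactly 0 for every f and D when no child changes.

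**4. Age limit.** 19 years × 12 = 228 months, so the limit in the vital-signs note coincides with the end of the SDS reference. Months from entry to the limit = 228 − 12 × entry age:

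| Entry age (years) | 17.9 | 17 | 16 | 15 | 12 |
|---|---|---|---|---|---|
| Months to limit | 13.2 | 24 | 36 | 48 | 84 |

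This route of loss affects only the oldest entrants, and only later windows. Stopping treatment can remove a child of any age.

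**5. What the other analyses give.**

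| Analysis | Within patient? | What it leaves open |
|---|---|---|
| Velocity SDS | Yes, per window | One 6-month step at a time; height and weight, not BMI; no value if the preceding window is empty |
| Raw height and weight change | Yes, per time point | Not age-standardised |
| BMI-for-age category change | Yes | Counts of category moves; no mean change per window |
| Shift to worst SDS | Yes | Three bands, no fixed time; a move from +1.6 to −1.6 stays in the normal band |
| Shift to last height SDS | Yes | Eight bands; mixes follow-up times; no BMI |
| LGG height model | Longitudinal | LGG height only |

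No row gives a cumulative paired change, at a given window, in HGG height SDS or in BMI SDS in either cohort.

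**The case against.** The strongest reply is that growth is already examined within patients in several ways. Velocity SDS is within patient, per window, and standardised for age and sex. Raw height and weight have paired change by time point. Height and BMI SDS have paired shift tables, and the height table has eight bands, so it is not coarse. The SAP itself calls the by-window comparison informal, and nothing is tested. All of this stands, and it limits the weight of the point.

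Some stronger readings therefore fail:

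- A reader might infer that growth is judged only by unpaired means, or that no within-patient change by window is planned. The velocity definition and the vital-signs section contradict both.
- A reader might infer that loss of patients necessarily shifts the mean. It does so in expectation only if leavers and stayers had different baseline SDS. Because SDS is already standardised for age and sex, a younger remaining group is not in itself a reason for a different mean.
- A reader might infer that later windows hold the children who did best. The documents give no such data.
- A reader might add that growth is a leading safety issue for this drug class. The documents do not say so, and growth is not among the listed adverse events of special interest.

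Two caveats also stand. That the baseline row contains all patients is inferred from the absence of a restriction. And sections 2.8.4.5 and 2.8.4.6 are not visible in the public text; the change log of the 2021 HGG SAP identifies them as puberty and bone age, so they are unlikely to supply the missing summary.

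What the reply does not remove is the gap in the comparison the SAP itself invites: it sets levels against baseline without matching the patients.

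**Conclusion.** The point holds in a limited form. In both final SAPs the by-window SDS rows are unpaired with baseline, and selective loss can move them without any change in growth. With a baseline difference of 0.5 SDS between stayers and leavers, the artefact is 0.13 to 0.38 SDS as the share remaining falls from 75% to 25%; across differences of 0.25 to 1.0 it runs from 0.06 to 0.75. These sizes rest on assumed values of f and D. If there is no difference, the expected artefact is zero and only chance movement remains.

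The gap is largest for BMI SDS in both cohorts and for height SDS in HGG; LGG height has the mixed model. The summary is descriptive safety output, and no test or primary conclusion depends on it. The change is worth making because it is nearly free and makes the invited comparison interpretable.

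**What to change.** In section 2.8.4.7 of both final SAPs, add for each on-treatment window, among patients with an SDS at baseline and in that window:

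- the mean (SD) and median within-patient change from baseline in height SDS and in BMI SDS;
- the baseline mean of those same patients beside it.

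State that the informal comparison with baseline rests on these columns. The number of patients is already a standard statistic under section 2.1 and need only be shown in each window.

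The cost is a few more columns from variables already derived. No visit, measurement, treatment or endpoint changes. The change does not recover children past 228 months, who have no SDS under either approach, but it stops their absence from being read as a change in growth.

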2.8.4.8 Ophthalmologic exam

Visual acuity will be converted from snellen to logMAR scale as defined in [Holladay 1997 (20)], and categorized as the following change from baseline:

- Improvement: $\geq 0.2 \log MAR$ improvement (decrease in logMAR)
- Stable: neither \geq 0.2 logMAR improvement nor worsening, where
- Worsening: $\geq 0.2 \log MAR$ worsening (increase in logMAR)

Visual acuity categories at each time point, as well as best and worst category on treatment will be presented.

2.8.4.9 Palatability

Data on palatability were analyzed at the time of primary analysis and no further data have been collected. The analysis of palatability data will not be repeated at the final analysis.

2.8.4.10 Additional analyses

Time to first occurrence

Time to first occurrence of an event is defined as time from start of study treatment to the date of first occurrence of this event (or first event within an AE grouping), i.e. time in days is calculated as (start date of first occurrence of event) - (start of study treatment) +1.

For Kaplan-Meier analyses of time to occurrence, in the absence of an event during the ontreatment period, the censoring date applied will be **the earliest** of the following dates:

- death date
- end date of on-treatment period

- data cut-off date
- withdrawal of informed consent date.

Failure curves (ascending Kaplan-Meier curves) will be constructed. Median together with 95% CI as well as 25th percentile and 75th percentile will be presented.

In addition, the median time to occurrence for the subset of patients who experienced the event of interest will be calculated. Simple descriptive statistics, median, min and max as well as 25th percentile and 75th percentile, will be presented.

[figure not shown]
